8.2. Secondary Efficacy Analysis

The secondary efficacy analysis will focus on DOR and PFS analysis in the study population (FAS analysis data set), as well as on subgroup analysis of ORR, PFS, and DOR in genetic sub-types (AITL, PTCL-NOS, CXCL12+, and Other).

The duration of the response will be calculated for subjects who achieve an objective response (either CR or PR, whichever comes first). For such subjects, the duration of the objective response is defined as the number of days from the start date of the objective response to the first date of either documented progressive disease or death. All efforts will be made to objectively define the endpoint by collecting the necessary data and reducing the likelihood of missing data. In the event of a maintained response, the DOR will be censored at the last evaluable non-PD assessment.

Disease progression will be determined by the investigator using the primary efficacy endpoint assessment. Progression free survival will be defined as the time (in months) from first dose (Cycle 1 Day 1) to the minimum date of progression or death, if death occurred within 126 days

³ Wilson, E. B. (1927). "Probable inference, the law of succession, and statistical inference". *Journal of the American Statistical Association*. 22 (158): 209–212.

⁴ Clopper, C.; Pearson, E. S. (1934). "The use of confidence or fiducial limits illustrated in the case of the binomial". *Biometrika*. 26 (4): 404–413.

of the last treatment or assessment. If the subject goes off study with no documentation of PD, the censoring date will be the date of the last evaluable assessment.

Sensitivity analyses may be conducted to explore the effect of different censoring on DOR and PFS.

The duration of the objective response and progression free survival will be analyzed using the Kaplan-Meier (KM) method. 95% CI for KM curve will be constructed using Greenwood's⁵ formula in the log-log scale.

The median DOR and PFS will be evaluated using the 50th percentile of KM distribution. 95% CIs for the median will be constructed based on a robust nonparametric method of Brookmeyer and Crowley⁶.

Summary tables and advanced data visualizations will be used for presenting KM plots, 95% CIs for probabilities of surviving X months, and a median survival estimate with its 95% CIs. The analysis will be conducted on FAS (primary) [REDACTED] populations.

Secondary analysis also involves subgroup analyses by genetic sub-types for ORR, DOR, and PFS. For each sub-type, the survival curves (DOR and PFS) and ORR rates will be estimated along with the relevant confidence intervals according to the methodology described above (Section 8.1 and Section 8.2).

Listings with participant level summary of DOR, such as treatment initiation date, progression date, first response date, durations, censoring status, best overall response, and analysis belonging to the population will be presented.

Multiple sensitivity analyses, as part of the exploratory analysis, may be conducted. Parametric survival regression framework (including Cox-regression and exponential regression) may be used to provide an alternative assessment of the survival curves and hazard function estimation. Sensitivity analysis may also include alternative methods for KM analysis (using interpolation estimators for median survival estimation, different methods for constructing CIs, etc.).

Parametric modelling may also be used for identification of potentially influential covariates and estimation of their impact. These exploratory analyses will be conducted as deemed appropriate.

Parametric modelling may be used to assess and compare the response in the subgroups of interest. A logistic regression framework may be used for ORR subgroups analysis. The models may be extended to control for influential covariates identified during the model building process. Parametric modelling (Cox regression) may also be used for subgroup analysis for DOR and PFS. As for the ORR case, the models may be extended to have influential covariates. Extensive data visualization will be used to present interval estimates of the response rate and survival summaries comparing the subgroups.

⁵ Greenwood, M. (1926). Reports on Public Health and Medical Subjects. Ministry of Health. No.33 pp. iv + 26 pp.

⁶ Brookmeyer, R.; Crowley, J. (1982). "A Confidence Interval for the Median Survival Time." *Biometrics* 38, no. 1: 29-41.

It should be noted that the subgroup analysis may encounter problems related to small sample sizes. These issues may potentially lead to degenerate estimation of median survival or quartile estimation (and to other estimation problems). Model based analysis may also suffer from small N limitations. It is critical to provide sensitivity analysis for all the main subgroup analysis as well as goodness of fit diagnostics and robustness testing whenever appropriate. All small sample size analysis may undergo stability analysis including data point perturbations. Alternative approaches, such as using interpolation-based estimation for median survival may be exercised for ensuring comprehensive sensitivity analysis.

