12.2 Endpoints

12.2.1 Efficacy

[figure not shown]
The objective response rate will be estimated for each tumor histology type evaluated. The estimate of the objective response rate will be calculated based on the maximum likelihood estimator (i.e., crude proportion of subjects whose best overall response is CR or PR). The estimate of the objective response rate will be accompanied by 2-sided 95% exact binomial confidence intervals.

The duration of objective response will be calculated for subjects who achieve CR or PR. For such subjects, the duration of objective response is defined as the number of days from the start date of PR or CR (whichever response is achieved first) to the first date that progressive disease is objectively documented. Disease progression will be determined by the Investigator using the Lugano Classification and/or mSWAT. The duration of objective response will be right-censored for subjects who achieve CR or PR and meet 1 of the following conditions: 1) non-protocol anticancer treatment started before documentation of disease progression, 2) death or documented disease progression after more than 1 missed disease assessment visit, or 3) alive and does not have documentation of disease progression before a data analysis cutoff date.

The duration of objective response will be summarized descriptively using the Kaplan-Meier method. The 50th percentile of the Kaplan-Meier distribution will be used to estimate the median response duration.

Progression free survival will be defined as the time (in months) from enrollment to either first observation of progressive disease or occurrence of death due to any cause within 126 days (approximately 2 time intervals for tumor assessments) of either first administration of tipifarnib or the last tumor assessment. In subjects without a progression date or with a death date more than 126 days after the first administration of study drugs or the last tumor assessment, the PFS time should be censored on the date of last tumor assessment or date of first administration of study tipifarnib. Progression free survival analyses should consider tumor assessments after treatment discontinuation or metastatic surgery.

The PFS will be summarized descriptively using the Kaplan-Meier method. The 50th percentile of the Kaplan-Meier distribution will be used to estimate the median PFS.

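### SAP 8.2 lets a late death end DOR while PFS is censored, omits the protocol's DOR censoring rules, and SAP 14 lists no change

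*SAP*

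**What the plan says.** SAP 8.2 runs DOR from the start of the response "to the first date of either documented progressive disease or death". Its only DOR censoring rule is: "In the event of a maintained response, the DOR will be censored at the last evaluable non-PD assessment". PFS runs from first dose to "the minimum date of progression or death, if death occurred within 126 days" of the last treatment or assessment, and "If the subject goes off study with no documentation of PD, the censoring date will be the date of the last evaluable assessment". A check on these choices is optional: "Sensitivity analyses may be conducted to explore the effect of different censoring on DOR and PFS".

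Protocol 12.2.1 runs DOR "to the first date that progressive disease is objectively documented". It right-censors DOR in three situations: "non-protocol anticancer treatment started before documentation of disease progression"; "death or documented disease progression after more than 1 missed disease assessment visit"; and a subject who is alive with no progression documented by the cutoff. Its PFS starts at enrollment and counts a death only within 126 days of first administration or the last tumor assessment.

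SAP 14 names four changes from the protocol: ORR not estimated by histology, an added exploratory efficacy analysis, added summaries of hematology and chemistry events, and no laboratory shift analysis. None concerns DOR or PFS.

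**The concern.** Response cannot begin before treatment does, so a subject's DOR should not outlast the same subject's PFS. Under SAP 8.2 it can, because death ends DOR at any time but ends PFS only inside a 126-day window. A responder who dies late is credited with months in which no scan showed that the response persisted. An otherwise identical survivor is censored at the last scan.

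Separately, progression or death after new therapy, or after a gap in scanning, is a DOR event on the SAP's wording and a censored observation under the protocol. A reader of the study report who relies on SAP 14 would believe that DOR follows the protocol. DOR is a secondary endpoint, reported overall and by subtype.

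**Working it through.** The point rests on definitions. The arithmetic shows when they diverge. All subjects below are hypothetical.

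1. **Scan days.** Assessments fall on Day 22 of Cycles 2, 4, 6, 9, 12 and 15 (Protocol 8.1). With 28-day cycles, day = 28 × (cycle − 1) + 22, giving days 50, 106, 162, 246, 330 and 414. The gaps are 56, 56, 84, 84 and 84 days.

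2. **The 126-day window.** Protocol 12.2.1 describes it as about two assessment intervals. Two intervals are 2 × 56 = 112 days in the 8-weekly phase and 2 × 84 = 168 days in the 12-weekly phase. So 126 is 126/56 = 2.25 early intervals or 126/84 = 1.5 late ones. It does not coincide with a rule based on missed visits.

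3. **Late death.** Take response on day 50, last dose on day 105, last scan on day 106 and no documented progression. The window closes on day 106 + 126 = 232.
   - Death on day 232: DOR event at 232 − 50 = 182 days; PFS event on day 232.
   - Death on day 233: DOR event at 233 − 50 = 183 days; PFS censored at day 106.
   - Identical subject still alive: DOR censored at 106 − 50 = 56 days.

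4. **Reach of step 3.** The death must be at least 127 days after the last assessment (127/30.4375 = 4.2 months), and also more than 126 days after the last treatment. The longest scheduled gap is 84 days, or 84 + 10 = 94 with opposite ±5-day windows. That is below 126, so a responder scanned on schedule is not exposed to this particular mismatch.

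5. **New therapy.** Take response on day 50, treatment stopped without progression, new therapy on day 60, and progression at the scheduled scan on day 106. The protocol censors DOR. The SAP as worded gives an event at 106 − 50 = 56 days. This responder was scanned on schedule.

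6. **Missed scans.** Take response and last scan on day 50, scans on days 106 and 162 missed, and progression found on day 246. The SAP gives a DOR event at 246 − 50 = 196 days and the protocol censors DOR. PFS is an event on day 246 under both documents.

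7. **Whether the protocol's missed-visit rule alone would cure step 3.** With the last scan on day 106, the next visits are days 162 and 246. If a visit counts as missed once its +5-day window closes (an assumption), two are missed only after day 251. If death is a DOR event, a death on days 233 to 251 would still be an event for DOR and censored for PFS. Death therefore needs its own limit, matched to PFS.

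8. **Other unlisted changes.** The PFS start moves from enrollment (Protocol 12.2.1) to first dose (SAP 8.2). The anchor of the 126-day window moves from first administration or last tumor assessment to last treatment or assessment. SAP 14 records neither.

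**The case against.** **Death is a usual DOR event, and the protocol is no model.** This stands in part. Protocol 12.2.1 never names death as a DOR event, gives no DOR censoring date, and already treats late events differently for DOR and PFS. Part of the mismatch therefore starts there, and counting death is not in itself the fault. What remains is a death rule without a limit beside a PFS rule with one, and no entry in SAP 14.

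**The protocol's censoring rules may still apply.** SAP 1 presents the SAP as an elaboration of the protocol. Protocol 9.12 withdraws a subject who needs a non-permitted treatment and allows use of the data obtained before withdrawal. A reader might infer that the SAP has abolished the new-therapy and missed-visit rules; silence does not prove that. But the inclusion of death is explicit, and the wording in 9.12 is permissive and sets no censoring rule.

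**Other SAP text covers it.** SAP 6.4 censors dropouts without confirming events, but a recorded death is an event. SAP 8.2 calls subgroup sensitivity analysis critical but names no censoring rule for it.

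**Such deaths may not be captured.** The text of Protocol 8.1, 10.1 and 11.7.1 starts survival contacts at progression, and the subject in step 3 has none. This limits how often the case arises. It does not make the rule coherent when a death date is on file.

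**Scans may continue.** Protocol 8.1 and 10.1 let scans stop at new therapy, while 11.7 and Table 1 (footnotes 8 and 19) continue them to progression. If they stop, the late-death case becomes possible; if they continue, the new-therapy case does.

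**Conclusion.** The rule is wrong as written and should be corrected. It can make the same death a DOR event while PFS is censored, with DOR longer than PFS. The SAP states neither of two protocol DOR censoring rules, and SAP 14 is silent on DOR and PFS.

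The size is known per subject only: in the examples, an event at 183 days where a survivor is censored at 56, and an event at 56 or 196 days where the protocol censors. Protocol 5.2 reports five responders among the evaluable subjects of each expansion cohort, so one reclassified subject would be one fifth of such a group. The final numbers are not given.

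Three stronger readings are not supported:
- A reader might infer that anyone scanned on schedule is safe. That holds only for the late-death mismatch; step 5 is the counter-example.
- A reader might infer that the SAP inflates median DOR. Late deaths add long event times, but progression soon after new therapy adds short ones. The documents give no counts of either, so the direction is unknown.
- A reader might infer that a test is compromised. DOR is descriptive and no test depends on it.

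**What to change.** 1. In SAP 8.2, state the Protocol 12.2.1 DOR censoring rules: new anticancer therapy before progression, and death or progression after more than one missed assessment. Set the censoring date at the last evaluable assessment before the new therapy or the gap. The protocol gives no date, so this is an addition. Say whether transplantation counts as new therapy.
2. State whether death is a DOR event. If it is, give it a time limit consistent with the PFS death rule, so that no death is an event for DOR and censored for PFS. Do not add new-therapy or late-progression censoring to PFS as part of this change: Protocol 12.2.1 has neither for PFS.
3. Name one DOR sensitivity analysis, overall and by subtype, that counts death at any time and counts progression or death after new therapy or missed visits.
4. List in SAP 14 every departure from Protocol 12.2.1: death as a DOR event, any change to DOR censoring, the PFS window anchor and the PFS start.

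The cost is SAP wording and re-derived censoring flags. The response, progression and censoring data (SAP 8.2) and the later-therapy and survival information (SAP 7.6) are already planned for listing. The downside is fewer DOR events, wider intervals and possibly informative censoring at new therapy, which the analysis in item 3 would show.

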8.3. Exploratory Efficacy Analysis

Exploratory analysis will be conducted as deemed appropriate. It will include sensitivity analysis described in Section 8.1 and Section 8.2. Exploratory analysis can be based on either or both FAS [REDACTED] data sets.

An analysis of overall survival to estimate median overall survival time and corresponding 95% confidence interval and provide per subject summary of overall survival will be conducted overall and for each subtype (AITL, PTCL-NOS, CXCL12+, and Other). Overall survival will be defined as the time (in months) from first dose (Cycle 1 Day 1) to the occurrence of death due to any cause. In subjects without a death date, the OS will be censored on 1) the date a subject has end of study reason of 'ended study per protocol' for subjects with no survival status documentation, or 2) the date a subject withdraws consent from study or is lost to follow-up, if there is no additional information. Subjects who ended study per protocol were no longer followed for survival status.

ORR, PFS, and DOR will be evaluated in the subgroups of partial and complete responders. Further analysis may be conducted to evaluate the impact of age, disease duration and severity, IPI scores, geography, and other potentially influential covariates on ORR, PFS, and DOR. This analysis will be conducted using parametric models – logistic for ORR and Cox-regression for PFS and DOR.

Tumor data may be analyzed using longitudinal mixed-effect models. Models will be explored to include covariates that can affect the tumor dynamics. Tumor data will also undergo subgroup analysis in AITL, PTCL-NOS, CXCL12+, and Other sub-populations. The analysis will be visualized using model summary plots, waterfall plots for maximum reduction in tumor lesion size, and spider plots to depict the reduction in tumor lesion by subject for the FAS [REDACTED] populations.

Biomarkers will be listed and may be further analyzed outside of this report.

Exploratory analysis may also include sensitivity analysis to the statistical methodology and stability analysis when a small sample is present.

Other exploratory analysis can be conducted as deemed appropriate.

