8.4 Removal of Subjects from Treatment or Assessment

Subjects may withdraw their consent to participate in this study at any time without prejudice. The Investigator must withdraw from the study any subject who requests to be withdrawn. A subject's participation in the study may also be discontinued at any time at the discretion of the Investigator and in accordance with his/her clinical judgment. Every effort should be made to complete, whenever possible, the tests and evaluations listed for the End of Treatment visit. The Sponsor must be notified of all subject withdrawals as soon as possible. The Sponsor also reserves the right to discontinue the study at any time for either clinical research or administrative reasons and to discontinue participation by an individual Investigator or site for poor enrollment or noncompliance.

Overall, the reasons for which the Investigator or Kura Oncology may withdraw a subject from study treatment include, but are not limited to, the following:

- Subject experiences disease progression
- Subject experiences unacceptable toxicity
- Subject requires more than 2 dose reductions
- Subject experiences toxicity that is deemed by the Investigator to be no longer safe for the subject to continue therapy
- Subject requests to withdraw from the study treatment
- Subject requires or has taken medication prohibited by the protocol
- Subject is unwilling or unable to comply with the study requirements
- Subject withdraws consent to collect health information
- Subject was erroneously admitted into the study or does not meet entry criteria
- Subject is lost to follow-up
- Subject becomes pregnant

Subjects will return for an End of Treatment visit within approximately 30 days after the last administration of the study drug (or sooner if another anticancer therapy is to be initiated). If a subject fails to return for scheduled visits, a documented effort must be made to determine the reason. If the subject cannot be reached by telephone after 2 attempts, a certified letter should be

sent to the subject (or the subject's legally authorized representative, if appropriate) requesting contact with the Investigator. This information should be recorded in the study records.

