11.7.1 Follow Up after Disease Progression

Upon disease progression, all subjects will be followed approximately every 12 weeks for survival and the use of subsequent therapy until either death or 12 months after accrual of the last study subject, whichever occurs first. Information on survival and subsequent anticancer therapy may be collected by phone.

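### The overall survival censoring rule has no last-known-alive fallback, so median OS can be biased upward where the recorded exit date falls after the last contact

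*SAP*

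**What the plan says.** SAP section 8.3 defines OS as the "time (in months) from first dose (Cycle 1 Day 1) to the occurrence of death due to any cause". For subjects without a death date it names two censoring dates:

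- "the date a subject has end of study reason of 'ended study per protocol' for subjects with no survival status documentation";
- "the date a subject withdraws consent from study or is lost to follow-up, if there is no additional information".

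The join between the two limbs reads "for subjects with no survival status documentation, or 2) the date a subject withdraws consent from study or is lost to follow-up": the first limb is for undocumented status, the second for withdrawal or loss.

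It adds: "Subjects who ended study per protocol were no longer followed for survival status". It gives no censoring date for subjects whose last record shows them alive.

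Protocol section 11.7.1 sets the contact schedule: once progression has occurred, "all subjects will be followed approximately every 12 weeks for survival and the use of subsequent therapy", ending at death or 12 months after the last subject is accrued. Protocol section 8.4 describes what a site does when a subject stops attending: "If the subject cannot be reached by telephone after 2 attempts, a certified letter should be" sent. Neither document says which date is then entered as the date of loss.

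Elsewhere the SAP stops the clock at the last observation. Section 8.2 censors PFS at the last evaluable assessment and DOR at the last such assessment without progression. Section 9 closes ongoing adverse events at the last contact date.

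**The concern.** The first limb applies by its own terms to subjects whose survival status is undocumented, yet it counts them as alive up to an end-of-study date. The second limb can do the same for a subject lost to follow-up, if the loss is dated after the last contact. A death in that interval would not be captured, while the interval itself is credited as survival.

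The interval need not be short. Survival contacts are about 12 weeks apart and start only at progression. Under Protocol section 8.1, a subject who stops treatment without progression and starts another anticancer therapy no longer needs tumor assessments, and section 11.7.1 gives no survival contacts before progression.

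At stake is the reported median OS. The study has no control arm (SAP section 3.5), so a bias in the estimate has no counterpart to cancel it, and this bias can only favor the drug. SAP section 8.2 mentions sensitivity to censoring for DOR and PFS. For OS there is only a general, optional provision in section 8.3.

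**Working it through.** The documents give no expected median, event count or power for OS, so there is no planned figure to reproduce.

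**Direction.** The Kaplan-Meier estimate is S(t) = product over death times t_j ≤ t of (1 − d_j/n_j), where d_j is the number of deaths and n_j the number at risk at t_j. Moving a censoring time later leaves every d_j unchanged and can only raise n_j at deaths between the old and new times. Each factor then stays equal or rises, so S(t) and its median cannot fall.

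**Size.** This was simulated, comparing the SAP date with last-known-alive censoring on the same simulated data.

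Inputs from the documents:
- N = 65 (SAP section 4).
- Study end 12 months after the last subject enrolls (Protocol section 8.6).
- Contacts every 12 weeks, i.e. 84/30.4375 = 2.76 months (Protocol section 11.7.1).
- One true median of 19.7 months, from the T-cell and Hodgkin group of the earlier phase 2 study (Protocol section 5.2).

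Assumptions not in the documents:
- Exponential survival, with 6 and 12 months as the other true medians.
- Uniform accrual over 54 months.
- 5%, 10%, 20% or 30% of subjects with undocumented status.
- Contact ending uniformly within 24 months (or by study end if sooner), taken back to the last 12-weekly contact.
- Recorded exit date 0, 12, 24 or 48 weeks after that contact, or at a study-wide cutoff.

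There were 1,500 runs per setting. Medians are in months, SAP rule against last known alive. Percentages come from unrounded medians.

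| Recorded date | Increase, all settings | True 12, 20% undocumented | True 19.7, 20% undocumented |
|---|---|---|---|
| At last contact | 0% | 11.9 vs 11.9 | 19.7 vs 19.7 |
| 12 weeks later | 1-5% | 12.4 vs 12.0 (3%) | 20.1 vs 19.5 (3%) |
| 24 weeks later | 1-9% | 12.7 vs 12.0 (6%) | 20.8 vs 19.7 (6%) |
| 48 weeks later | 1-17% | 13.2 vs 12.0 (10%) | 21.9 vs 19.8 (10%) |
| Study-wide cutoff | 2-29% | 13.4 vs 12.1 (11%) | 23.2 vs 19.7 (18%) |

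The largest value is the cutoff scenario with 30% undocumented and a true median of 19.7 months: 25.8/20.0 − 1 = 29%.

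Last-known-alive censoring gave 5.9-6.1, 11.8-12.2 and 19.5-20.0 months for true medians of 6, 12 and 19.7.

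**Reading the last row.** Mean follow-up to the cutoff is 54/2 + 12 = 39 months, and contact ends on average by month 12 at the latest. The built-in gap therefore averages at least 39 − 12 = 27 months, or 27/2.76 = about 10 contact intervals. This row is an upper bound and does not show what 12-weekly contacts would produce.

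**The case against.** The strongest reply is that the rule may do no harm. Survival contacts begin only at progression, so a subject who reaches study end without progression could lack survival status documentation while still attending visits and scans. Both documents foresee subjects with sustained benefit at study end moving to other means of continued treatment. For them the end-of-study date lies close to an attended visit and the bias is near zero. This stands as a possibility: the SAP does not say which subjects the first limb covers.

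Three stronger readings are tempting, and the documents do not support them:

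- A reader might infer that loss to follow-up is dated when it is declared. Protocol section 8.4 describes the failed contact attempts but not the date recorded.
- A reader might take the end-of-study date to be a study-wide cutoff. The SAP ties it to the individual subject's end-of-study reason.
- A reader might treat the withdrawal and loss dates as unconditional. They apply only when there is no additional information. Consent withdrawal is normally itself a contact and adds little or no bias.

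The qualifier does not close the gap, however. It allows other information to be used but names no date to fall back on, and it is attached to the second limb.

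The simulation also draws loss of contact independently of prognosis, so the near-exact recovery under last-known-alive censoring is partly built in. If subjects who are deteriorating lose contact sooner, that rule is biased too.

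Finally, OS is not a listed objective or endpoint in either document and carries no hypothesis or decision rule. The planned per-subject summary and the follow-up listings would let a reader see the dates.

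**Conclusion.** The point holds in a limited form. The OS rule lacks a last-known-alive fallback, leaves subjects documented alive without a censoring date, and departs from the SAP's own handling of PFS, DOR and ongoing adverse events. Where the recorded date is later than the last contact, median OS is either unchanged or too high.

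The documents do not show that it will be too high, or by how much. That depends on three things they do not state: how many subjects are affected, the gap, and which date is recorded for a loss. On the assumptions shown, the plausible increase runs from zero to a few percent for a 12-week gap and up to 9% for 24 weeks. An inflation of 20% to 30% needs a cutoff-like date and a large undocumented share, so it is a bound and not an expectation.

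These sizes are for all 65 subjects. In a subtype of 12 the median moves in coarse steps and may not change at all. The primary ORR analysis and the secondary PFS and DOR analyses are unaffected.

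**What to change.** Replace both limbs in SAP section 8.3 with one rule: every subject without a death date is censored at the last date documented alive, whatever the end-of-study reason. That date is the latest of any attended visit, dose, scan, laboratory sample or survival contact. The rule also covers subjects documented alive.

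State which date the eCRF holds for loss to follow-up. Report how many subjects have a recorded exit date later than their last documented contact, and the size of that gap. Keep the present rule, if at all, as a sensitivity analysis.

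The cost is a change of SAP wording before database lock and one derived variable from dates already collected. Where the exit date was a contact, the result does not change. Otherwise the reported OS may be slightly less favorable. The new rule still assumes that loss of contact is unrelated to prognosis, and the report should say so.
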